### **7.2 VE Subgroup Estimates**

In addition to testing the consistency of vaccine efficacy across the subgroups, estimates of VE within the subgroups will be obtained using the Clopper-Pearson method for the binomial proportion from which an exact 95% CI for VE will be derived. These estimates will be obtained on the PP population.

Estimates of VE within the subgroup of Cohort will also be provided for the ITT population. Also, estimates of VE and exact 95% CI by subtype (Type A/H1N1 and Type A/H3N2) or by lineage (Type B/Yamagata) and Type B/Victoria) will be provided if sufficient data is available. Descriptive statistics will be provided for all subgroups including influenza sub-type or lineage.

## **8. ASSESSMENT OF STUDY POPULATION**

### **8.1 Disposition of Subjects**

The number and percent of subjects will be summarized for the following categories: subjects screened, screening failed, enrolled subjects, enrolled and not randomized, randomized subjects, completed, and discontinued.

Reasons for screen failure will be summarized in the screened population.

All subjects who fail to complete the study will be categorized by their primary reason for discontinuation and summarized by group. Disposition of subjects and reasons for withdrawal will also be summarized separately. Supportive listings will be provided.

The number and percent of randomized subjects with protocol deviations and the number of protocol deviations will be summarized by group, broken down by main deviation category (major/minor) and sub-categories in the randomized population. Subjects will be counted once per deviation category, and can be counted for more than one deviation category.

In addition to the number of subjects included in each analysis set (Safety, ITT, PP), will be summarised overall and by group.

### **8.2 Demographic and Baseline Characteristics**

Analyses of demographic and baseline characteristics will be performed on the ITT, PP and safety populations.

Standard descriptive statistics will be presented at least for the continuous variables of:

- Age (years)
- Height (cm)
- Weight (kg)
- BMI (kg/m^2)

The total counts and percentages of subjects will be presented at least for the categorical variables of:

- Cohort
- Age (<65 years, ≥ 65 years)
- Sex
- Race
- Ethnicity

### **8.2.1 Medical History**

Medical history is defined as any condition that started prior to the ICF signature at V1. Medical history will be coded using Medical Dictionary for Regulatory Activities (MedDRA) version 21.0 and listed separately by group, System Organ Class (SOC) and Preferred Term (PT) within SOC.

Percentage of subjects with any medical history will be summarised for the ITT analysis set overall, by SOC and PT.

### **8.2.2 Prior and Concomitant Medications**

Prior and concomitant medications are collected in the CRF at each study visit. A prior medication has started and ended prior to the first vaccine dose. A concomitant medication has started on or after the first study vaccine dose or is continuing after the first vaccine dose.

Any medications with an unknown start or stop date will be assumed to be concomitant medications, unless a partial start date or stop date indicates otherwise.

Medication terms will be coded according to WHO Drug Dictionary 01Mar2018.

Table summaries will be provided for prior and concomitant medications; a further distinction between concomitant medications starting after first vaccination and continuing medications will be done.

Previous vaccination history will be summarised similarly. The presence of severe vaccination reactions that occurred during previous vaccination will be summarized by SOC, PT for the subjects having received previous vaccinations.

## **8.3 Duration of Follow-Up**

Duration of follow-up defined for the flu season (cohorts 1 and 2) as the time (in days) between the first dose of vaccination and last date at which the subject answered to the center call, last date of site visit, last date of phone contact, date of early discontinuation visit, or date of death for subjects known to have died (whichever comes last).

The distribution of days under active surveillance, i.e., the number of days between the date of last vaccination day + 14 and the date where the last call was answered within the active surveillance period will be summarised overall and by group.

The distribution of days until last contact, i.e., the number of days between the date of last vaccination day + 14 and the date where the last call was answered within the active surveillance period or last phone contact (received by subject or representative) or last visit will be summarised overall and by group.

## 8.4 Vital Signs

Systolic and diastolic blood pressure (BP), Pulse, Respiratory Rate, and Body Temperature recorded at Visit 1 will be summarized overall and by group for the safety population.

## 8.5 Vaccine Received By Subject

The number and percentage of subjects who received one or 2 doses of vaccine will be presented. The distribution of time between the 2 vaccinations will be described.

# 9. DETAILS ON MISSING DATA

## 9.1 Handling of Missing Dates for Adverse Events

The following imputation rules apply to cases in which the start date is incomplete (i.e., partial or completely missing) for adverse events. In addition to the following rules, if the stop date is complete and the imputed start date is after the stop date, then the start date will be imputed using the stop date. If the stop date is on or after the date of first dose of vaccine in the study, but the start date is completely missing, then the start date will be imputed with the date of first dose of vaccine. If the stop date is prior to the date of first dose of vaccine in the study, but the start date is completely missing, then the start date will be imputed with the stop date.

For start dates with missing day and month (year is present):

- If the year of the incomplete start date is the same as the year of the date of the first dose of IP, then the day and month of the date of the first dose of vaccine will be assigned to the missing fields.
- If the year of the incomplete start date is prior to the year of the date of the first dose of vaccine, then December 31 will be assigned to the missing fields.
- If the year of the incomplete start date is after the year of the date of the first dose of vaccine, then January 1 will be assigned to the missing fields.

For start dates with missing month only (day and year are present):

- The day will be treated as missing and both month and day will be replaced according to the above procedure.

For start dates with missing day only (month and year are present):

- If the month and year of the incomplete start date are the same as the year and month of the date of the first dose of vaccine, then the date of the first dose of vaccine will be assigned to the missing day.
- If either the year of the incomplete start date is before the year of the date of the first dose of vaccine or if both years are the same but the month is before the month of the date of the first dose of vaccine, then the last day of the month will be assigned to the missing day.

- If either the year of the incomplete start date is after the year of the date of the first dose of vaccine or if both years are the same but the month is after the month of the date of the first dose of vaccine, then the first day of the month will be assigned to the missing day.

## **9.2 Handling of Missing Dates for Solicited Systemic and Injection Site Reactions**

For the analysis of solicited systemic and injection site reactions, missing dates will not be replaced. The denominator will be the number of subjects who returned their diary card for the period of assessment. Missing responses on the card will be treated as if no event occurred.

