3.2. Study Outcome Measures

3.2.1. Primary Outcome Measures

Safety

- Occurrence of vaccine-related SAEs from the time of the first study vaccination (M-001 or placebo) until end of first passive surveillance period
- Occurrence of NOCIs from the time of the first study vaccination (M-001 or placebo) until end of first passive surveillance period
- Occurrence of solicited injection site and systemic reactogenicity events on the day of each study vaccination through 8 days after each study vaccination (day of the vaccination inclusive)
- Occurrence of unsolicited AEs from the time of first study vaccination through 22 days after each study vaccination (day of the vaccination inclusive)
- Occurrence of all SAEs, regardless of the assessment of relatedness, from the time of receiving the first M-001 study vaccination until end of first passive surveillance period

Clinical Efficacy

- Percentage of either qRT-PCR or culture-confirmed influenza cases in the M-001 experimental group vs. placebo (during period of ≥ 15 days after the second vaccination until epidemiological levels of influenza are low as defined by the medical director) caused by any influenza A or B virus in association with a protocol defined Influenza Like Illness (ILI is defined as symptoms that include one of the respiratory symptoms (sore throat, cough, sputum production, nasal discharge or congestion, wheezing or difficult breathing) and at least one additional systemic symptom [fever (oral temperature $>37.2^{\circ}\text{C}$ for age 50-59, or $>36.7^{\circ}\text{C}$ for age 60 or more, or increased $\geq 1.3^{\circ}\text{C}$ from baseline), headache, myalgia and/or arthralgia, chills, and fatigue (tiredness for at least 12 hours)]. NP or combined nasal and throat swab will be collected from participants who meet the ILI definition within 24 hours from ILI being reported to or identified by study personnel for qRT-PCR analysis of influenza A and/or B virus. PCR confirmed samples will be further analyzed for culture confirmation.

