11.5.4. Missing Values and Outliers

All attempts will be made to collect all data per protocol. As missing data are expected to be minimal, no imputation will be performed for missing values. Any data point that appears to be erroneous or inexplicable based on clinical judgment will be investigated as a possible outlier. If data points are identified as outliers, sensitivity analyses will be performed to examine the impact of including or excluding the outliers. Any substantive differences in these analyses will be reported.

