### 4.4 Safety Endpoints Analysis

#### Local and Systemic Reactogenicity Events – Overall Summaries

Each set of tables described below will summarize the occurrence of events over the 3 following periods:

- P1. any day over 8-day period following first or second vaccination (Period = Day of the first/second vaccination to 7 days post first/second vaccination)
- P2. any day over 8-day period following first vaccination (Period = Day of the first vaccination to 7 days post first vaccination)
- P3. any day over 8-day period following second vaccination (Period = Day of the second vaccination to 7 days post second vaccination)

Summary of all the local and systemic reactogenicity **solicited** events provided for

- any local or systemic reactogenicity solicited events,
- any local events and by local event separately (5 events: blue spot/bruising, induration/swelling, redness/warmth, itching, pain/tenderness),
- any systemic reactogenicity events and by systemic reactogenicity event separately (14 events: decreased blood pressure/dizziness, chills/sweating, joint/muscle pain, headache, nasal congestion/runny nose/phlegm production/rhinitis, difficulty breathing/wheezing, general malaise/fatigue/loss of appetite, swelling/tender lymph nodes, irritability, rash, cough, sore throat, abdominal pain/diarrhea/nausea/vomiting, pruritus or itching on the body).

During the first season, fever was one of the solicited symptom and was graded subjectively as mild, moderate, or severe by the subject in addition to the oral body temperature daily record. This symptom was not recorded as such during the season 2019-2020. For homogeneity of reporting, oral body temperature daily records only will be presented for the 2 seasons and a separate table summarizing fever as a solicited symptom will be presented for season 2018-2019.

The tables will present the number and percentage of subjects with any events, the percentage in each table being computed using the number of subjects having received the specified vaccination and with diary data reported for local and systemic reactogenicity in the period of interest as defined in P1, P2, and P3.

For each of the above tables, the number and percentage of subjects will be tabulated by treatment.

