The percentage of subjects with any local or systemic reactogenicity solicited events overall and by vaccination will be compared between the groups using the chi-square test. Within-group comparison between the percentage of subjects with any local or systemic reactogenicity solicited events after first and second vaccination will be performed using Mc Nemar test.

Descriptive tables for duration of event will also be provided by solicited event.

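### SAP 9.2 scores blank diary responses as no event in a primary safety outcome, against the protocol's no-imputation rule and the denominator in SAP 4.4, without declaring the change

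*SAP*

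**What the plan says.** Protocol 3.2.1 lists among the primary safety outcomes: "Occurrence of solicited injection site and systemic reactogenicity events on the day of each study vaccination through 8 days". SAP 3.1 repeats this outcome.

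On missing data, Protocol 11.5.4 states: "As missing data are expected to be minimal, no imputation will be performed for missing values". The only sensitivity analysis in that section concerns outliers: "If data points are identified as outliers, sensitivity analyses will be performed to examine the impact of including or excluding the outliers".

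SAP 9.2 sets two rules for diary data. The denominator: "The denominator will be the number of subjects who returned their diary card for the period of assessment". The blanks: "Missing responses on the card will be treated as if no event occurred". SAP 4.3 also bases the percentages on returned cards. SAP 4.4 instead takes subjects who received the vaccination "with diary data reported for local and systemic reactogenicity in the period of interest".

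SAP 4.4 compares the arms by chi-square on the percentage with any local or systemic solicited event. The within-group comparison "after first and second vaccination will be performed using Mc Nemar test". Five local and 14 systemic symptoms are also tabulated one by one, and the table list in SAP section 12 includes first-versus-second-vaccination tables by symptom.

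Neither SAP section 11 nor the overview of changes at the front of SAP version 2.0 mentions the rule for blanks.

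**The concern.** Setting a blank to no event is a deterministic imputation, and it works in one direction only. A subject who had a reaction but left the item blank stays in the denominator and leaves the numerator. The reader of the safety tables would see a rate that looks complete, with no count of the blanks beneath it and no alternative analysis.

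The SAP also gives programmers two denominators that disagree. A returned but wholly blank card counts as event-free under SAP 9.2 and 4.3, and drops out under SAP 4.4.

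At stake are the accuracy of the reported reactogenicity rates and, if completeness differs between the two doses, the comparison of reactogenicity after dose 1 and dose 2.

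**Working it through.** There is no plan figure to reproduce: the documents give no expected reaction rate, no share of blank responses and no power for this outcome. All rates below are assumptions chosen to show scale.

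**1. Rates.** Let p be the true rate among subjects who returned a card, and m the share of event subjects whose event is lost because every response that would show it is blank. The rule reports p × (1 − m).
- p = 30%: 0.30 × 0.98 = 29.4%; 0.30 × 0.95 = 28.5%; 0.30 × 0.90 = 27.0%.
- p = 10%: 9.8%, 9.5% and 9.0% for the same m.

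If blanks are unrelated to events, a denominator of subjects with responses returns p. If 5% of all subjects have a blank record and p = 30%, the bounds are 28.5% (all blanks no event) and 28.5% + 5% = 33.5% (all blanks an event).

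**2. Between arms.** With a true 30% versus 20% and 5% loss in both arms, the table shows 28.5% versus 19.0%. The difference shrinks from 10.0 to 9.5 points; the ratio stays at 1.5.

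**3. Dose 1 versus dose 2.** Assume a true 30% at each dose, 18% with the event at both doses, and 1,900 pairs (Protocol synopsis: 2,027 M-001 subjects in cohort 1). With losses m1 and m2, independent of each other:
- both = 0.18 × (1 − m1) × (1 − m2)
- b = 0.30 × (1 − m1) − both
- c = 0.30 × (1 − m2) − both
- expected z = (b − c) × √1900 / √(b + c)

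Results, with no true dose difference:
- m1 = m2 = 5%: b = c, so z = 0.
- 2% and 5%: both = 0.1676, b = 0.1264, c = 0.1174, z ≈ 0.8.
- 2% and 10%: both = 0.1588, b = 0.1352, c = 0.1112, z ≈ 2.1.

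The rejection rate at two-sided 0.05 was also computed by normal approximation, with an assumed within-subject correlation of 0.4. This gives 0.09 + 0.4 × 0.21 = 17.4% with the event at both doses when p = 30%.
- Equal loss (5% and 5%): 0.05 at 2,000 or 6,000 pairs.
- 2% and 5%: 0.13 at 2,000 pairs, 0.28 at 6,000.
- 2% and 10%: 0.56 at 2,000 pairs, 0.96 at 6,000.

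Equal loss does not inflate the error rate, but it weakens a real difference slightly. For a true 30% versus 28% at 6,000 pairs, 5% loss at both doses takes power from 0.88 to 0.84.

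**4. Do the documents show unequal blanks?** No. They make it possible. The dose 1 diary is reviewed on site at Visit 2. The dose 2 diary is issued in a stamped envelope and reviewed by phone unless the subject comes to the site for Visit 3 (Protocol 7.2.1 and 8.1). Cohort 1 has no Visit 3 (Protocol Table 3). Cohort 2, about 8,000 subjects, has diary review at Visit 3 (Protocol Table 4).

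**The case against.** **A blank may be a non-report rather than a missing value.** Protocol 11.5.2 summarises the proportion of subjects who report each symptom, so the rule could be read as part of the outcome definition. This is arguable, but SAP 9.2 itself calls these responses missing, Protocol 11.5.4 covers missing values without exception, and the clash with the SAP 4.4 denominator remains.

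**The loss formula needs a lot of blankness.** One recorded positive day keeps the subject as a case. For the any-event rows, every other item must be negative or blank too. Unreturned cards are already excluded, and posting mainly threatens return rather than completeness. This stands, and makes the larger values of m less likely for the any-event test. It is weaker for the symptom-by-symptom tables, where other symptoms cannot make up for a blank row.

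**Important events have a second route.** Solicited events that are severe, need a physician or last beyond day 7 must also be recorded as AEs or SAEs (Protocol 9.2.2; SAP 4.1). This stands: the loss mainly concerns milder, short reactions.

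**A denominator of responders is not guaranteed unbiased.** If subjects fill in only the rows for symptoms they had, it drops true negatives and inflates rates. The diary layout is not in the documents, so both analyses need to be shown.

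A reader might also see a double standard, because SAP 4.2.1 imputes missing AE intensity as severe and missing causality as related. That comparison is not like for like: those rules fill in an attribute of an event already reported. The nearer parallel is missing severity of a solicited event, which SAP 4.2.3 and 4.4 leave missing.

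**Conclusion.** The point holds as a conflict between documents, an undeclared analysis rule and a one-directional effect on rates. Among card returners the rule cannot raise a reactogenicity rate. The shortfall is p × m: 0.6 to 3.0 points at an assumed 30% with 2% to 10% of event subjects affected, and close to nothing if missing data are as few as the protocol expects. The plan has no table that would show which case applies.

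Two stronger readings are not supported. The first is that the dose comparison is biased as it stands. McNemar keeps its error rate when loss is equal at both doses; distortion needs unequal blanks, and the documents give no missingness data by dose. Even then the result turns on the assumed gap, with z about 0.8 at 2% versus 5% and about 2.1 at 2% versus 10%. The second is that the rule favours the vaccine over placebo. It lowers rates in both arms, equal loss leaves the ratio unchanged, subjects are blinded, and nothing in the documents suggests that blanks differ by arm.

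**What to change.** - In SAP 4.4 and 9.2, define the denominator for each symptom as subjects with at least one recorded response for that symptom in the 8-day period. For the any-event rows, use subjects with at least one recorded response to any solicited item.
- Run McNemar on subjects with responses after both doses.
- Report the number of blank responses by arm and dose.
- Keep missing-as-no-event as a sensitivity analysis, shown beside a worst-case bound that counts blanks as events.
- Reconcile Protocol 11.5.4 with SAP 4.3, 4.4 and 9.2, and declare any retained departure in SAP section 11.

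No new data are needed. The cost is some extra table programming. Reported rates may become slightly less favourable, or slightly too high if subjects leave rows blank for symptoms they did not have. Blank days within a partly completed row would still count as event-free, and the table footnote should say so.

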# **10. GENERAL PRINCIPLES FOR REPORTING RESULTS**

## **10.1 Statistical Testing**

No adjustment of the Type I error for multiple comparisons will be made in the study; indeed, all analyses, estimations are supportive to the results of the primary endpoint.

### **10.1.1 Presentation of Results**

All analyses will use SAS® version 9.3 or higher. Unless otherwise specified, summary tables will be presented by vaccine group, labelled as follows: M-001 and Placebo.

All data will be presented in listings, sorted by country, site number and subject number, and group. Continuous variables will be summarised by the number of observations, mean, standard deviation, median, minimum, and maximum. Categorical variables will be summarized by frequency counts and percentages for each category. Unless otherwise stated, percentages will be calculated out of the population total for the corresponding group.

The minimum and maximum will be reported to the same number of decimal places as the raw data recorded in the database. The mean, median, and standard deviation will be reported to one more decimal place than the raw data recorded in the database. The maximum number of decimal places presented for any statistic shall be four.

Percentages will be presented to one decimal place except if percentage are smaller than 0.1%.

All confidence intervals (CIs) will be two-sided 95% CIs, unless stated otherwise, and presented to one more decimal place than the raw data recorded in the database. If a model is used to estimate the treatment difference, the corresponding CI according to the model will be presented. Otherwise, the unadjusted CI will be used. Nominal p-value will be presented for the main efficacy variable, but these cannot be interpreted in terms of statistical significance.

The presentation of p-values will be to three decimal places unless a p-value is less than 0.001, in which case “<0.001” will be displayed.

A month is operationally defined to be 30.4 days. A year defined to be 365 days.

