11.1. Study Hypotheses

The null hypothesis of vaccine efficacy (VE) equals 40% against the alternative hypothesis $VE > 40\%$ will be tested using the two-sided, 95% Clopper-Pearson confidence interval for VE. If the lower bound of the 95% confidence interval is above 40%, adequate efficacy will have been established.

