### 3.4 Study Design

This is a pivotal, multicenter, randomized, modified double-blind, placebo-controlled phase 3 trial to assess the safety and clinical efficacy of M-001, an influenza vaccine administered intramuscularly twice (2 doses 21 to 30 days apart) in older adults and the elderly ( $\geq 50$  years of age) who meet all eligibility criteria.

The study sample size of 12,000 subjects is based on the lower bound of the two-sided 95% confidence interval for vaccine efficacy (VE) being above 40% with 80% probability when true VE is 62%. It assumes 1:1 randomization, a 2.41% attack rate in the study population, and no more than 10% of subjects lost to follow-up or excluded from the per protocol population. Under these assumptions, 182 first episodes of qRT-PCR-confirmed influenza of any strain occurring at least 15 days after the second dose of study vaccine or control and prior to the end of the first influenza season will be needed to demonstrate efficacy is at least 40%.

A total of up to 10 sites are selected to participate to the Cell Mediated Immunity (CMI) substudy. A total of 350 subjects are randomly chosen among 700 subjects from the selected sites: approximately 263 subjects selected at random from 350 M-001 subjects and approximately 87 from 350 placebo subjects; placebo subjects being selected to maintain the study blind. Assuming that among the 263 M-001 selected subjects, 210 will have valid measurement for the change from baseline in percentage of CD4+ lymphocytes producing Th1 cytokine (e.g. INF- $\gamma$ ) in response to any of the 9 peptides in M-001, then this endpoint can be estimated with a precision of at most 2% (1/2 width of the 95% CI).

The trial spans 2 influenza seasons. In each of the 2 cohorts corresponding to season 2018-2019 and 2019-2020, subjects are randomized in a 1:1 ratio to receive two doses (on Day 0 and 22) of either M-001 or saline placebo prior to start of the influenza season.

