## **5.4 Efficacy Endpoints Analysis Methods**

### **5.4.1 Hypothesis**

The hypothesis to be tested is:  $H_0 : VE \leq 40\%$

where VE denotes the vaccine efficacy of M-001 against qRT-PCR- or culture-confirmed influenza in association with protocol-defined ILI over a first season of influenza.

The hypothesis will be rejected and the superiority of M-001 demonstrated if the lower bound of the two-sided 95% CI for VE is  $>40\%$  for the primary per-protocol analysis.

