### **5.4.2 Statistical Methods**

#### **Primary efficacy endpoint:**

The main analysis will be performed using data from cohort 1 (Season 2018-2019) and cohort 2 (Season 2019-2020) combined.

Efficacy will be assessed for the qRT-PCR- or culture-confirmed influenza caused by any influenza A or B virus in association with a protocol-defined ILI. The vaccine efficacy (VE) is defined as

$VE = 1 - [p_V/p_P]$ , where  $p_V$  and  $p_P$  are the proportions of subjects with qRT-PCR or culture-confirmed influenza caused by any influenza A or B virus in association with a protocol-defined ILI in the M-001 experimental group and placebo group, respectively.

For the main analysis performed on the PP set,  $p_V = C_V / N_V$  with  $N_V$  = number of subjects in the PP set in vaccine M-001 group and  $C_V$  = number of cases of qRT-PCR- or culture-confirmed

influenza in association with a protocol-defined ILI in the set of  $N_V$  subjects, and similarly for the placebo group with  $p_P = C_P / N_P$ .

The two-sided confidence interval for VE will be calculated by an exact method conditional on the total number of cases in both groups. VE can also be written as

$$VE = 1 - \left[ \frac{N_P}{N_V} x \frac{q}{1-q} \right], \text{ where } q = \frac{C_V}{C_V + C_P}.$$

Given the total number of cases, an exact confidence interval for  $q$  can be derived by the exact Clopper-Pearson method for the binomial proportion from which an exact 95% CI for VE can be derived.

The exact 95% CI for  $p_V$  and  $p_P$  within each group will be derived using the Clopper-Pearson exact method.

The conditional binomial test is testing about the probability an event falls in the vaccine rather than placebo group ( $q = \frac{C_V}{C_V + C_P}$ ).

The p-value resulting from the test of  $H_0: q \leq 0.6 * N_V / (0.6 * N_V + N_P)$  versus  $H_a: q > 0.6 * N_V / (0.6 * N_V + N_P)$  will be reported (test will be performed at the one-sided level 0.025).

The p-value of the exact test will be reported together with the exact 95% CI for the VE.

The main analysis performed on the PP set will be supported by an analysis on the ITT set. For the ITT set,  $N_V$  and  $N_P$  correspond to the number of subjects in the ITT set in the M-001 and placebo groups, respectively.

VE and 95% CI will be provided by cohort, age group, and combination of cohort and age group as well for the PP and ITT population.

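### SAP 10.1.1 calls the primary efficacy p-value nominal and not interpretable as significance, which contradicts the one-sided 0.025 test in SAP 5.4.2; no other p-value carries that label

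*SAP*

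**What the plan says.** Four places in the SAP and one in the protocol bear on the status of the primary test.

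- **SAP 5.4.1** sets the null hypothesis that vaccine efficacy (VE) is at most 40%, and the decision rule on the per-protocol (PP) set: "The hypothesis will be rejected and the superiority of M-001 demonstrated if the lower bound of the two-sided 95% CI for VE is" above 40%.
- **Protocol 11.1** gives the same rule: "If the lower bound of the 95% confidence interval is above 40%, adequate efficacy will have been established".
- **SAP 5.4.2**, primary efficacy endpoint, gives the p-value form of this test, conditional on the total number of cases. It fixes the level ("test will be performed at the one-sided level 0.025") and says "The p-value of the exact test will be reported together with the exact 95% CI for the VE".
- **SAP 10.1** says "No adjustment of the Type I error for multiple comparisons will be made in the study" and gives as the reason that the analyses are supportive to the primary endpoint result.
- **SAP 10.1.1**, on presentation of results, says "Nominal p-value will be presented for the main efficacy variable, but these cannot be interpreted in terms of statistical significance".

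**The concern.** A p-value from a pre-specified test at a stated level is a significance statement. SAP 5.4.2 sets up such a test for the primary endpoint, and SAP 10.1.1 says its p-value may not be read that way. If both are followed, the report could show an interval that meets the success rule next to a p-value from the same test that the SAP calls uninterpretable.

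The nominal label would fit the other p-values. SAP 10.1 leaves them all unadjusted, yet the label is attached only to the main efficacy variable. Nothing then tells an author not to present a secondary or subgroup p below 0.05 as a significant finding.

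**Working it through.** **1. Inputs.** Null VE 40%, true VE 62%, 1:1 allocation and 182 cases (SAP 3.4); one-sided level 0.025 and the exact conditional binomial method (SAP 5.4.2). Equal PP arms are assumed.

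**2. Conversion to the case split.** Let q be the probability that a case falls in the vaccine arm. With equal arms, q = (1 − VE) / [(1 − VE) + 1].

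- Null: q0 = 0.60 / 1.60 = 0.375
- Alternative: q1 = 0.38 / 1.38 = 0.2754

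**3. The plan's own figure.** SAP 3.4 describes the lower limit as "being above 40% with 80% probability when true VE is 62"%. With X distributed binomial(182, q), the largest c with P(X ≤ c | q0) ≤ 0.025 is c = 55. The exact one-sided error is 0.0242. Power is P(X ≤ 55 | q1) = 0.815. The stated 80% with 182 cases therefore reproduces.

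**4. Are the p-value and the interval the same test?** Lower VE limit = 1 − U / (1 − U), where U is the Clopper-Pearson upper 97.5% limit for q.

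| Vaccine cases of 182 | VE estimate | U | Lower VE limit | One-sided p |
|---|---|---|---|---|
| 55 | 1 − 55/127 = 56.7% | 0.3745 | 40.1% | 0.0242 |
| 56 | 1 − 56/126 = 55.6% | 0.3802 | 38.6% | 0.0347 |

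The two forms change verdict at the same case. Across the possible splits at 100, 150, 182, 200 and 260 total cases, the decision from p ≤ 0.025 and the decision from the lower limit never disagreed (0 mismatches). The p-value is another expression of the confirmatory rule, not a looser companion to it.

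**5. Where the nominal label is and is not.**

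| p-value | SAP section | Adjusted? | Called nominal? |
|---|---|---|---|
| Primary VE, exact test | 5.4.2 | Not needed (single primary test) | Yes, in 10.1.1 |
| Culture-confirmed VE (secondary) | 5.4.2 | No | No |
| Illness duration, Cochran-Mantel-Haenszel | 5.4.2 | No | No |
| Exploratory proportions, Fisher | 5.4.2 | No | No |
| Subgroup homogeneity, Breslow-Day | 7.1 | No | No |
| Solicited events and temperature, chi-square and McNemar | 4.4 | No | No |

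**6. Direction of the hypotheses in SAP 5.4.2.** The text prints H0: q at or below 0.6·N_V / (0.6·N_V + N_P), against q above it. Efficacy beyond 40% means fewer vaccine cases, hence q *below* that value. Take 50 vaccine cases of 182, so VE = 1 − 50/132 = 62.1%:

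- matching the interval rule: P(X ≤ 50 | 0.375) = 0.0028
- as printed: P(X ≥ 50 | 0.375) = 0.998

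Any edit that points to the 5.4.2 test as confirmatory must therefore correct its direction as well.

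**The case against.** The strongest reply is that success is declared from the interval, in both SAP 5.4.1 and Protocol 11.1, and that SAP 10.1.1 restricts only the p-value. That is correct. A reader might infer that the SAP contradicts its own success rule or abandons its confirmatory test. The documents do not support this: someone following the SAP as written still decides from the lower limit, with the same boundary and power. What remains is the conflict between 10.1.1 and 5.4.2.

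A second reply is that SAP 10.1 already calls the other analyses supportive, so they are not without any caveat. This also stands in part. Supportive describes the role of an analysis; it does not say that its p-value is nominal.

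A third is that 10.1.1 may mean only the ITT or subgroup analyses of the main variable. The sentence does not say so and does not exempt the primary PP test.

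A reader might also be tempted to count the unadjusted tests and turn the count into a familywise false-positive rate. The planned tests do not support such a figure. Many overlap (each dose and either dose; overall and within cohort), some compare doses within an arm, Fisher's test is conservative for rare outcomes, and a simple count misses the Cox and Poisson analyses. They also serve no single claim.

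**Conclusion.** The concern holds in a limited form. SAP 10.1.1 is wrong as written: it denies a significance reading to the one p-value that SAP 5.4.2 sets up as a test at one-sided 0.025, and that test is equivalent to the interval rule. The unadjusted secondary, exploratory, subgroup and reactogenicity p-values are nowhere called nominal.

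The effect on the trial's decision is nil. At 182 cases with equal PP arms, success still requires at most 55 vaccine cases, and power at a true VE of 62% is 81.5%. Unequal arms would move q0, but the p-value and the interval would move together, so the equivalence does not rest on that assumption. What is at stake is how the pivotal p-value and the non-primary p-values are presented and read.

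**What to change.** Replace the SAP 10.1.1 sentence with: *The primary PP analysis of VE (lower bound of the two-sided exact 95% CI above 40%, section 5.4.1; equivalently the exact test at one-sided 0.025) is the confirmatory test. All other p-values are nominal and cannot be interpreted as statistical significance.*

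In the same edit, correct the hypotheses in SAP 5.4.2 to H0: q ≥ 0.6·N_V / (0.6·N_V + N_P) versus Ha: q < that value, so that the reported p-value agrees with the interval.

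When adopting the wording, note that Protocol 11.5.3 attaches the same 40% criterion to a Cox model if discontinuation or loss to follow-up differs by group, whereas SAP 5.4.2 treats the Cox model as a sensitivity analysis. The new sentence makes the Cox p-value nominal, so that difference should be acknowledged in SAP section 11.

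The cost is a short text change in two SAP sections and one line in a third. Sample size, case target, level and success boundary do not change.
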